6.11.4.4.2 RBC Transfusion

The same analyses of any rescue will be performed for RBC transfusion by narrow and broad separately.

6.11.4.4.3 ESA Rescue

The same analyses of any rescue will be performed for RBC transfusion by narrow and broad separately. In addition, the increases in dose relative to last dose will be characterized in three categories by percentage increase: <50%, ≥50% and <100%, and ≥100%. Subjects will be presented by their maximum category of increase within each analysis periods.

6.12 SAFETY ANALYSES

All analyses of the safety data will be summarized by treatment group and overall based on the safety population unless otherwise specified.

6.12.1 Adverse Events

A treatment-emergent adverse event (TEAE) is one that begins or worsens after treatment initiation. TEAEs will be summarized using the number and percentage of subjects with TEAEs for all subjects in the safety population.

All AEs will be coded by MedDRA. The MedDRA version used for reporting this study will be described in a footnote on AE related outputs. TEAEs will be summarized by SOC and PT for each treatment group. All TEAE summaries will provide the number of subjects reporting at least 1 TEAE. TEAE summaries will be ordered by decreasing pooled percentage for SOC, and PT within SOC.

An overall summary table will show number of subjects with at least 1 of each of the following:

- TEAE
- Drug-related TEAE
- Severe TEAE
- Treatment-emergent SAE
- Drug-related treatment-emergent SAE
- TEAE leading to withdrawal of study drug
- Drug-related TEAE leading to withdrawal of study drug
- Fatal TEAE
- All Deaths: Any deaths reported during the study no matter whether deaths are caused by TEAEs

Summaries by SOC and PT will be provided for the following types of TEAEs:

- TEAE
- TEAE by severity
- Drug-related TEAEs (including all categories for relationship to study medication other than “Unrelated”, as determined by the investigator)
- Treatment-emergent serious adverse event (SAE)

-
- Drug-related treatment-emergent SAE
 - TEAEs leading to withdrawal of study drug
 - Drug-related TEAE leading to withdrawal of study drug
 - Fatal TEAE
 - Adverse events of special interest (AESI) listed on [Appendix E](#)

A summary by treatment group and PT will be presented for TEAEs reported by at least 5% of subjects in either treatment group.

TEAEs will be summarized by 1) worst severity, and 2) worst causality by SOC and PT. For each subject and each PT, the worst severity recorded will be used in the by-severity summaries. Similarly, the worst causality (most related to treatment) attributed will be used in the by-causality summaries. If severity or causality is missing, data will be imputed to the worst category.

Treatment-emergent SAEs and deaths will be summarized by treatment group and overall, including the number and percentage for subject with Treatment-emergent SAEs, number of deaths (all causes, resulting from adverse events). Summary by SOC and PT will include subjects affected by Treatment-emergent SAEs, occurrence (all, causally related to treatment), number of death (all causes), and deaths causally related to treatment.

A by-subject listing of all TEAEs will be provided. This listing will be presented by treatment group and will include center, subject identifier, age, sex, race, AE (SOC, PT, and verbatim term), study day of onset, study day of resolution, duration, severity, seriousness, relationship to the study medication, action taken, outcome and causality.

A by-subject listing of all Aes happening before first dose date will be provided.

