4.7 Secondary Safety Endpoints

Secondary endpoints include the following:

- Proportion of subjects receiving RBC transfusions from Baseline to Week 26.
- Proportion of subjects receiving RBC transfusions from after Week 26 to Week 52.
- Proportion of subjects with Hb >11.0, Hb >12.0, >13.0, or >14.0 g/dL.
- Proportion of subjects with Hb <7.0, <8.0, <9.0, or <10.0 g/dL.
- Proportion of subjects with Hb increase >1.0 g/dL within any 2-week interval or >2.0 g/dL within any 4-week interval.

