8.1.2 Permanent Discontinuation of Study Medication

Subjects who permanently discontinue study medication prior to study completion will not continue in the study. These subjects are to have their ET visit at the time of permanently discontinuing study medication and perform a 4-week safety follow-up after ET visit.

Subjects may permanently discontinue study medication for any of the following reasons:

- AE
- Investigator's discretion
- Subject withdrawal of consent
- Lack of efficacy
- Lost to follow up despite reasonable efforts by the Investigator to locate the subject
- Death
- Other reasons (pregnancy, kidney transplantation, specific reasons to be documented by the Investigator)

Lack of efficacy is defined as an inadequate response to vadadustat in the Investigator's opinion.

Subjects who undergo a solid organ (including kidney), hematopoietic stem cell, or bone marrow transplantation will have vadadustat permanently discontinued.

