9.1.4 Safety Follow-up

The safety follow-up will be conducted 4 weeks after the EOT visit, or 4 weeks after the last dose of study medication for ET.

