10.5.7 Remaining Safety Endpoints

The analysis of the safety endpoints will be detailed in the SAP: The analysis of proportion of subjects with Hb >11.0, Hb >12.0, Hb>13.0, or >14.0 g/dL post-Baseline will classify a subject as a “yes” if:

- Any value Hb >11.0 g/dL at any time after Day 1
- Any value Hb >12.0 g/dL at any time after Day 1
- Any value Hb >13.0 g/dL at any time after Day 1
- Any value Hb >14.0 g/dL at any time after Day 1
- Any value Hb <7.0 g/dL at any time after Day 1
- Any value Hb <8.0 g/dL at any time after Day 1
- Any value Hb <9.0 g/dL at any time after Day 1
- Any value Hb <10.0 g/dL at any time after Day 1

The analysis of proportion of subjects with any Hb increase >1.0 g/dL within any 2-week interval or >2.0 g/dL within any 4-week interval post-Baseline will classify a subject as a “yes” if at least 1 of the following criteria at any point after Day 1 is met:

- Hb increase >1.0 g/dL within any 2-week interval
- Hb increase >2.0 g/dL within any 4-week interval.

Subjects with no available data post-Baseline will be excluded from this analysis. All other subjects will be classified to the “no” category.

Observed values of continuous and categorical parameters and changes from Baseline for continuous parameters to each study visit will be summarized descriptively for vital signs and clinical laboratory results.

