6.11.4.4.1 Analysis of Rescue

The number and percentage of subjects receiving rescue by rescue type, treatment group and analysis period will be summarized. Confidence interval will be 95% CI for these proportions along with the difference in proportions as well as the odds ratio. A Mantel-Haenszel test stratified by the dialysis organization will be used to calculate the 95% CI for the statistics of treatment comparison.

Time to first rescue therapy administration by narrow and broad definitions separately will be estimated using the Kaplan-Meier product-limit method and log rank test. Subjects without events will be censored at last dose date. The hazard ratio and corresponding 95% CI for the comparison of vadadustat to Mircera will be estimated using a Cox proportional hazards model, with treatment group, randomization stratification factor (dialysis organization), and baseline Hb as covariates. Kaplan-Meier plots of time to first rescue will be provided.

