6.12.2 Laboratory Data

6.12.2.1 Hb-related Safety Endpoints

Hb-related safety endpoints will be defined using data from the central laboratory. No imputation will be performed for missing data. For each endpoint in [Table 3](#), the proportion of the study group who satisfy the definition and 95% CI for these proportions will be reported along with the difference in proportions as well as the odds ratio; a Mantel-Haenszel method stratified by the dialysis organization will be used to calculate the 95% CI for the statistics of treatment comparison.

Table 3. Hb-related Safety Endpoints from First Dose Date to Last Visit

Variable	Criterion for “Yes”
Hb >11.0 g/dL	Any Hb >11.0 g/dL at any time after Day 1
Hb >12.0 g/dL	Any Hb >12.0 g/dL at any time after Day 1
Hb >13.0 g/dL	Any Hb >13.0 g/dL at any time after Day 1
Hb >14.0 g/dL	Any Hb >14.0 g/dL at any time after Day 1
Hb <7.0 g/dL	Any Hb <7.0 g/dL at any time after Day 1
Hb <8.0 g/dL	Any Hb <8.0 g/dL at any time after Day 1
Hb <9.0 g/dL	Any Hb <9.0 g/dL at any time after Day 1
Hb <10.0 g/dL	Any Hb <10.0 g/dL at any time after Day 1
Hb increase >1.0 g/dL within any 2-week interval	Difference between 2 Hb values within any 2 weeks >1.0 g/dL after Day 1
Hb increase >2.0 g/dL within any 4-week interval	Difference between 2 Hb values within any 4 weeks >2.0 g/dL after Day 1

Note: Subjects without any post-baseline data will be excluded from this analysis.

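### Adverse-event, death and Hb-excursion proportions ignore follow-up time; if more vadadustat subjects stop early, common events unrelated to exit would look too favourable to vadadustat

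*SAP*

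**What the plan says.** **Adverse events and deaths.** SAP 6.12.1: "TEAEs will be summarized using the number and percentage of subjects with TEAEs for all subjects in the safety population". SAEs, AESIs and deaths are likewise counts or percentages. The section gives no person-time, cumulative incidence or confidence interval.

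**Hb excursions.** The SAP heading is "Table 3. Hb-related Safety Endpoints from First Dose Date to Last Visit", so the window closes at each subject's own last visit. A subject is a yes if any central-laboratory value after Day 1 meets the criterion. Arms are compared by stratified Mantel-Haenszel difference and odds ratio. For the Hb-rise criteria, protocol 10.5.7 states: "Subjects with no available data post-Baseline will be excluded from this analysis. All other subjects will be classified to the" no category. The threshold rows work the same way, so a subject who leaves early without an excursion counts as event-free.

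**End of observation.** Protocol 8.1.2: "Subjects who permanently discontinue study medication prior to study completion will not continue in the study". Protocol 9.1.4: "The safety follow-up will be conducted 4 weeks after the EOT visit, or 4 weeks after the last dose of study medication for ET". The transplantation paragraph of protocol 9.11.1.1 instead has transplant subjects stop drug and carry on with the Schedule of Activities, while citing 8.1.2. The two passages must be reconciled.

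**Where the SAP does use time.** Treatment discontinuation has Kaplan-Meier, log rank and Cox analyses (SAP 6.5). So does rescue: "Time to first rescue therapy administration by narrow and broad definitions separately will be estimated using the Kaplan-Meier product-limit method and log rank test". The rescue methods extend to RBC transfusion (SAP 6.11.4.4.2), so the protocol safety endpoint "Proportion of subjects receiving RBC transfusions from Baseline to Week 26" is outside this point. Liver, potassium and blood-pressure findings are tabulated by analysis period.

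**The concern.** A crude proportion compares arms fairly only if the arms are observed for similar lengths of time. Here, observation length depends on staying on drug, and some reasons to stop apply to one arm only. Protocol 8.1.2 states "Lack of efficacy is defined as an inadequate response to vadadustat", and the liver stopping rules in protocol 7.1.3 name vadadustat alone. Control subjects remain on a drug they already take.

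In the sponsor's earlier conversion study (CI-6548-0025, protocol 3.4), 60.5% of vadadustat and 88.9% of epoetin subjects completed treatment; 76.7% and 94.4% completed the study. If anything similar happened here, the tables could not separate a lower event rate from a shorter observation time. Safety is part of the primary objective, and protocol 3.5.3 calls this the first study to give dialysis-dependent subjects TIW vadadustat for more than 20 weeks.

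**Working it through.** **The plan's own figures.** The plan states no expected event risk. Its only design calculation is noninferiority power with one common 30% dropout: 150 × 0.7 = 105 per arm; SE = 1.2 × √(2/105) = 0.1656; Φ(0.75/0.1656 − 1.96) = 99.5%, consistent with the stated >90%. That bears on the primary test, not on safety. The 30% is not split by arm.

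**Inputs from the documents.** 52 weeks of treatment; 4 weeks of AE follow-up; about 300 pooled vadadustat and 150 Mircera subjects; completion 60.5% vs 88.9% or 76.7% vs 94.4%; 30% dropout.

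**Assumptions.** Event hazards constant and equal in both arms (true ratio 1.00). Exit independent of the event. Completion figures from a study dosed to Week 20 used as 52-week values. Event risks of 6% to 90% are illustrative.

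**Formulas.** Exit hazard l = −ln(completion)/52. Event hazard h = −ln(1 − risk)/52. Follow-up after stopping is f = 4 weeks for AEs and 0 for Hb.

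Crude risk = 1 − e^(−hf) × [ l/(l+h) × (1 − e^(−52(l+h))) + e^(−52(l+h)) ]

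SE = √(pv(1−pv)/300 + pm(1−pm)/150)

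**Worked case: AE, 30% risk, completion 60.5% vs 88.9%.** h = 0.006859, l = 0.009664 and 0.002263, e^(−4h) = 0.9729.
- Vadadustat: 1 − 0.9729 × [0.5849 × (1 − 0.4235) + 0.4235] = 25.99%.
- Mircera: 1 − 0.9729 × [0.2481 × (1 − 0.6223) + 0.6223] = 30.34%.
- Difference −4.35 points; SE 4.53; 0.96 SE.

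| Completion, vadadustat vs Mircera | Endpoint, 52-week risk | Crude % | Ratio | Difference (points) | Size in SE |
|---|---|---|---|---|---|
| (a) 60.5 vs 88.9 | AE, 6% | 5.18 vs 6.11 | 0.848 | −0.93 | 0.40 |
| (a) | AE, 15% | 12.97 vs 15.24 | 0.851 | −2.27 | 0.65 |
| (a) | AE, 30% | 25.99 vs 30.34 | 0.857 | −4.35 | 0.96 |
| (a) | AE, 90% | 80.83 vs 88.84 | 0.910 | −8.0 | 2.3 |
| (a) | Hb, 50% | 40.43 vs 47.49 | 0.851 | −7.1 | 1.4 |
| (b) 70 vs 88.9 | AE, 6% | 5.51 vs 6.11 | 0.901 | −0.61 | 0.26 |
| (c) 76.7 vs 94.4 | AE, 6% | 5.73 vs 6.28 | 0.912 | −0.55 | 0.23 |
| (d) 70 vs 70 | any | equal | 1.000 | 0 | 0 |

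A 90% risk is realistic for any TEAE: protocol Table 2 gives 88.3% and 89.3% in Study CI-6548-0017 (follow-up length not given there).

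**Range on the 20-week assumption.** If the treatment-completion figures instead ran on at constant hazard from Week 20, 52-week completion would be 0.605^2.6 = 27.1% vs 0.889^2.6 = 73.6%. An AE with a 30% risk over 56 weeks would then differ by −8.0 points (18.4% vs 26.4%). With the imbalance reversed (10% of vadadustat and 30% of Mircera subjects stopping), the same event shows +2.8 points, against vadadustat.

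**Events tied to exit.** In a simulation where the event itself triggers exit in 90% of affected vadadustat subjects, crude risks are 28.6% vs 28.5%: no bias. For a low-Hb row at 6% risk in (a), if none, half or all of the excess vadadustat exit comes only after the event, the crude ratio is 0.835, 0.912 or 1.000.

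**Does the remedy have its own bias?** Yes.
- *Early-peaking hazard* (scenario (a), AE, equal true hazards): 3 times higher for 12 weeks gives a rate ratio of 1.05 (crude 0.89); 5 times higher for 20 weeks gives 1.08 (crude 0.91).
- *Informative exit* (Hb, 6%): let half the subjects have 0.5 and half 1.5 times the average hazard, with all excess vadadustat exit in the low-hazard half. Completion there is 2 × 60.5 − 88.9 = 32.1%. The crude ratio is 0.91, the rate ratio 1.11, and the Kaplan-Meier cumulative-incidence ratio 1.12 (6.67% vs 5.96%).

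**The case against.** **Unequal stopping is not shown for this trial.** This stands. The earlier study dosed to Week 20, had a Week 12 criterion for continuing on TIW, another comparator, another dose range (150 to 900 mg, against 300 to 1200 mg TIW here) and only 129 vs 36 subjects. Stopping drug there evidently did not end participation, since more subjects completed the study than completed treatment. Its figures make an imbalance plausible and do not size it.

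**The bias is within sampling error.** This holds for AEs at risks up to 30% in scenario (a), where it stays below 1 SE. It does not hold for common endpoints.

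**The information is already planned.** Exposure duration (SAP 6.10), time to discontinuation (SAP 6.5) and listed onset days would reveal an imbalance. Reporting of related AEs after the reporting period (protocol 9.11.5) and the permitted search of public records for survival (protocol 8.1.6) reduce the loss slightly. None of these corrects the comparison.

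**The remedy can be worse.** This stands in part: under the informative exit shown above, both supportive methods err further from 1 than the crude ratio, in the opposite direction. They can only be supportive.

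**The absence may lie in unseen text.** SAP 6.13 and most of the appendices are blacked out, and the table shells are separate. The point is limited to the visible 6.12.1 and 6.12.2.1, which refer to no such method.

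**Conclusion.** The concern holds conditionally. The visible plan has no follow-up-adjusted summary for AEs, deaths or Hb excursions. If vadadustat subjects stop more often, crude proportions for events unrelated to exit will favour vadadustat. Under scenario (a), with the assumptions listed, the effect is minor for uncommon events and reaches 2.3 SE for an AE with 90% risk and 1.4 SE for an Hb row with 50% risk. It matters mainly for any TEAE and, if that row proves common here, Hb >11.0 g/dL.

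A reader might infer three stronger things that the documents do not support:
- *The safety tables will favour vadadustat.* They give no arm-specific discontinuation for this trial, and equal stopping gives a ratio of 1.000.
- *Every row is biased the same way.* Four of the ten Table 3 rows are low-Hb thresholds that may be tied to exit for lack of efficacy; their direction is unsettled.
- *Exposure-adjusted estimates are the correct answer.* They assume exit unrelated to event risk, and rates also assume a roughly constant hazard.

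No planned test or decision rule changes. What is at stake is how the safety tables are read.

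**What to change.** Keep the crude tables. In SAP 6.12.1 and 6.12.2.1, prespecify as supportive, for pooled vadadustat vs Mircera with 95% CIs and no multiplicity claim:

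1. exposure-adjusted first-event rates per 100 subject-years;
2. cumulative incidence at Weeks 26 and 52, with death as a competing event (Kaplan-Meier for all-cause death).

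Apply both to any TEAE, any SAE, all-cause death, the SAP Appendix E AESI categories and the ten Table 3 rows. Time at risk ends at first event or end of safety follow-up. For Hb it ends at first event or last central-laboratory sample, because the follow-up visit may be by telephone. State the assumptions on exit and hazard, note that low-Hb rows may be tied to exit, and say that these estimates are read together with the crude percentages. Reconcile protocol 8.1.2 with the transplantation paragraph of 9.11.1.1 so that the end of time at risk is defined for those subjects.

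The cost is extra tables from dates already collected, with no new visits or data. The downside is that the supportive estimates may themselves mislead if exit is informative or hazards peak early.

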6.12.2 Laboratory Data

6.12.2.1 Hb-related Safety Endpoints

Hb-related safety endpoints will be defined using data from the central laboratory. No imputation will be performed for missing data. For each endpoint in [Table 3](#), the proportion of the study group who satisfy the definition and 95% CI for these proportions will be reported along with the difference in proportions as well as the odds ratio; a Mantel-Haenszel method stratified by the dialysis organization will be used to calculate the 95% CI for the statistics of treatment comparison.

Table 3. Hb-related Safety Endpoints from First Dose Date to Last Visit

Variable	Criterion for “Yes”
Hb >11.0 g/dL	Any Hb >11.0 g/dL at any time after Day 1
Hb >12.0 g/dL	Any Hb >12.0 g/dL at any time after Day 1
Hb >13.0 g/dL	Any Hb >13.0 g/dL at any time after Day 1
Hb >14.0 g/dL	Any Hb >14.0 g/dL at any time after Day 1
Hb <7.0 g/dL	Any Hb <7.0 g/dL at any time after Day 1
Hb <8.0 g/dL	Any Hb <8.0 g/dL at any time after Day 1
Hb <9.0 g/dL	Any Hb <9.0 g/dL at any time after Day 1
Hb <10.0 g/dL	Any Hb <10.0 g/dL at any time after Day 1
Hb increase >1.0 g/dL within any 2-week interval	Difference between 2 Hb values within any 2 weeks >1.0 g/dL after Day 1
Hb increase >2.0 g/dL within any 4-week interval	Difference between 2 Hb values within any 4 weeks >2.0 g/dL after Day 1

Note: Subjects without any post-baseline data will be excluded from this analysis.

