g. Serum pregnancy will be tested in women of childbearing potential at SV2. Additional serum or local urine pregnancy tests may be conducted throughout the study as determined by the investigator to establish the absence of pregnancy during the study. If positive at SV2, the subject is not eligible to enter the study. If a subject becomes pregnant during the study, the subject must permanently discontinue study medication.																
h. For eligibility, 2 Hb values measured by the central laboratory during Screening (SV1, SV2 or retest) must be between 8.5 and 11.0 g/dL (inclusive).																
i. Iron indices: ferritin, iron, TIBC, and TSAT.																
j. Liver function tests: total bilirubin, ALP, ALT/SGOT, AST/SGPT, and LDH.																
k. Lipids: total cholesterol, LDL, HDL, and triglycerides.																
l. The coagulation tests prothrombin time, partial thromboplastin time, and international normalized ratio will be performed for unscheduled visits only.																
m. Optional additional blood samples will be collected for PGx and future biospecimen research for consenting subjects only.																
n. Most recent dialysis adequacy assessment.																
o. Subjects will be provided with a supply of vadadustat at the Baseline visit and will be resupplied at subsequent visits as needed. Refer to the study drug dispensing instructions for further details.																

Study Period	Screening		Treatment (Conversion and Maintenance)												Safety Follow-up ^a					
	Visit Type	SV1	SV2	BL	Primary Efficacy Evaluation						Secondary Efficacy Evaluation									
Week	-8 to 0		0		2	4	6	8	12	16	20	24	26	30	34	38	42	46	50	52 (EOT) /ET ^b
Visit Window (Days)					±3				±5			±3	±5						±3	+7

q. Vadarustat PK samples will be taken predose (within 60 minutes) and 0.5 hours ±5 minutes, 1, 2 and 3 hours ±10 minutes postdose.

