6.0 STUDY POPULATION

6.1 Inclusion Criteria

Subjects must meet the following inclusion criteria:

1. ≥ 18 years of age.
2. Receiving chronic, outpatient in-center hemodialysis TIW for end-stage kidney disease for at least 12 weeks prior to SV1.
3. Currently maintained on Mircera (≤ 250 $\mu\text{g}/\text{month}$) with at least 2 doses received within 8 weeks prior to SV2.
4. Mean screening Hb between 8.5 and 11.0 g/dL (inclusive), as determined by the average of 2 Hb values measured by the central laboratory at least 4 days apart between SV1 and SV2.
5. Serum ferritin ≥ 100 ng/mL and transferrin saturation (TSAT) $\geq 20\%$ during Screening.
6. Folate and vitamin B₁₂ measurements \geq lower limit of normal during Screening.

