6. STATISTICAL METHODOLOGY AND ANALYSES

6.1 GENERAL CONSIDERATIONS

Data collected throughout the study will be summarized using descriptive statistics and listed in by-subject listings. Continuous variables will be summarized using number of subjects with data, mean, standard deviation (SD), median, minimum, and maximum. For categorical variables, the number and percentage of subjects in each category will be tabulated. Summaries will be provided by treatment group and for vadadustat treatment groups combined within appropriate analysis populations, and by time point/time period, as appropriate.

For Hb, Baseline will be calculated as the average of the last 2 central laboratory Hb measurements of samples taken at or prior to the first dose. For blood pressure, baseline will be calculated as the average of the blood pressure within same visit, and then select

the last available results on or prior to the first dose. For other parameters, unless otherwise specified, Baseline will be defined as the last available value prior to the first dose of study medication.

The primary efficacy endpoint as well as the secondary and all other efficacy endpoints will be summarized using descriptive statistics by treatment group, and by analysis visit and/or analysis period as appropriate. Mean values of Hb and selected other efficacy parameters will be plotted across analysis visits/periods by treatment group.

Hb values will be assessed through the central laboratory for dose adjustments, efficacy, and safety evaluations.

If the central laboratory uses assays that have lower limits of detection (LLD), all laboratory results below the LLD will be imputed with the LLD. Results reported as greater than a value (i.e., “> value”) will be imputed as 1.5 x that value.

Mircera will be converted to IV epoetin equivalent unit per kilogram per week (U/kg/week) as 1:220. The conversion has been derived from published literature ([Paganini, 1995](#); [Kaufman1998](#)[Levin, 2008](#)[Wright2015](#)) and input from clinical experts.

Study days are defined as follows:

Study Day = [Event date – First dosing date + 1], if on or after first dosing date
[Event date – First dosing date], if before first dosing date.

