6.14 SUBGROUP ANALYSES

The same analyses of the primary efficacy endpoint and secondary efficacy endpoint will also be performed for subgroups based on the following. Subgroup analyses will be performed only if the total number of outcomes in a stratum, combined over the two treatment groups, is at least 30.

- Dialysis organization [USRC (U.S. Renal Care), ARCRS (American Renal Clinical Research Services), Frenova (Frenova Renal Research)]
 - Age (<65 years, \geq 65 years)
 - Sex (Male, Female)
 - Race (White, Black, All others)
 - Baseline Hb (<10.0 g/dL, \geq 10.0 g/dL)

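### The Hb <10.0 g/dL safety endpoint ignores Baseline Hb although entry allows values from 8.5 g/dL, so it mixes low entry Hb with new falls and loses sensitivity

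*SAP*

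**What the plan says.** Protocol 6.1 admits subjects with "Mean screening Hb between 8.5 and 11.0 g/dL (inclusive"). A footnote to the Schedule of Activities (Protocol 1.3) applies the same range to the two values themselves; the floor is 8.5 g/dL either way.

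The proportions with Hb <7.0, <8.0, <9.0 and <10.0 g/dL are secondary safety endpoints (Protocol 4.7, SAP 5.5). SAP Table 3 scores them on "Any Hb <10.0 g/dL at any time after Day 1", "Any Hb <9.0 g/dL at any time after Day 1" and so on. Protocol 10.5.7 has the same rule: "Any value Hb <10.0 g/dL at any time after Day 1". The only exclusion is in the note to Table 3: "Subjects without any post-baseline data will be excluded from this analysis".

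The arms are compared by risk difference and odds ratio, using a Mantel-Haenszel method stratified by dialysis organization only. A Baseline Hb value exists (SAP 6.1: "Baseline will be calculated as the average of the last 2 central laboratory Hb measurements"), and SAP 6.14 already splits it at 10.0 g/dL. That split serves efficacy only: "The same analyses of the primary efficacy endpoint and secondary efficacy endpoint will also be performed for subgroups".

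**The concern.** Two of the four low-Hb thresholds, 9.0 and 10.0 g/dL, lie inside the entry range. A subject who enters at 9.6 and improves to 9.8 at Week 2 is scored as Hb <10.0, exactly like a subject who enters at 10.8 and falls to 9.8. Table 3 cannot tell them apart.

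This matters more here than in many trials. Protocol 9.11.1.1 says that worsening anemia is not an adverse event unless its cause is something other than the subject's CKD, so the adverse-event tables will largely miss it. The protocol's own background (3.4) also reports that 6 of 31 subjects (19%) on 450 mg TIW withdrew for worsening anemia, against 0 of 30 and 1 of 33 on the two daily regimens. A threshold table that responds weakly to new falls is less useful for a question the program has reason to ask.

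**Working it through.** **The plan's own figure.** The documents give no expected rate or power for the low-Hb endpoints. The only power figure (SAP 3.3, >90%) is for the primary noninferiority test and does not bear on this point. It holds: 150 × 0.70 = 105 per arm; SE = 1.2 × √(2/105) = 0.166; 0.75/0.166 = 4.53; power = Φ(4.53 − 1.96) = 99.5%.

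**How many start below the line (assumed distributions).** For a normal distribution truncated to 8.5–11.0 g/dL, with mean 9.8 to 10.4 and SD 0.5 to 0.7:
- P(<10.0) runs from 0.24 (mean 10.4, SD 0.5) to 0.66 (mean 9.8, SD 0.5).
- P(<9.0) runs from 0.003 (mean 10.4, SD 0.5) to 0.10 (mean 9.8, SD 0.7).

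**How many of these are scored (simulation, all inputs assumed).** The Schedule of Activities gives 16 post-Baseline Hb values to Week 52. Assumptions: entry Hb uniform or truncated normal on 8.5–11.0 (means 9.5, 10.0, 10.3; SD 0.6–0.7); within-subject SD 0.3, 0.5 or 0.7; Hb flat, or rising to 10.5 by Week 8 or Week 20.
- Of those below 10.0 at entry, 89% to 100% are scored, including when Hb later rises to 10.5; 58% to 92% are scored at Week 2 alone.
- They supply 35% to 83% of all <10.0 cases.
- Of those below 9.0 at entry, all are scored if Hb stays flat, but only 24% to 91% if it rises to 10.5.
- Of those at or above 10.0 at entry, 53% to 99% are also scored.

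**Dilution.** Let a fraction b start below 10.0 and all be scored in both arms. The Table 3 difference is then (1 − b) × the new-fall difference. Assume new falls in 70% vs 55% of the rest (15 points, odds ratio 1.91):

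| b | Table 3 proportions | Difference | Odds ratio |
|---|---|---|---|
| 0.3 | 79% vs 68.5% | 10.5 points | 1.73 |
| 0.5 | 85% vs 77.5% | 7.5 points | 1.65 |

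For <9.0, b is 0.003 to 0.10, so the same formula loses at most 10% of the difference.

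**Sensitivity.** Same rates, 300 pooled vadadustat vs 150 Mircera, no dropout, SE = √(p₁q₁/n₁ + p₂q₂/n₂), power = Φ(d/SE − 1.96):
- b = 0.3, all subjects: 0.105/0.0446 = 2.35, power 65%. Restricted to 210 vs 105 at or above 10.0: 0.15/0.0579 = 2.59, power 74%.
- b = 0.5, all subjects: 0.075/0.0398 = 1.88, power 47%. Restricted to 150 vs 75: 0.15/0.0686 = 2.19, power 59%.

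Stratifying by Baseline category gives the same power as restricting. The low stratum then has zero difference and zero variance, so the stratified estimate and its SE are both the high-stratum values times one weight, and their ratio is unchanged. The estimate itself stays at 10.5 or 7.5 points.

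**Chance imbalance.** The SE of the between-arm difference in the already-low fraction is √[b(1 − b)(1/300 + 1/150)]: 4.6 points at b = 0.3 and 5.0 at b = 0.5. The pooled new-fall rate is (2 × 70% + 55%)/3 = 65%. A 5-point imbalance therefore moves the unadjusted difference by about 5 × (1 − 0.65) = 1.75 points.

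**The case against.** The strongest reply is that any occurrence is a legitimate endpoint. Protocol and SAP agree on it, dosing aims at 10.0 to 11.0 g/dL (Protocol 7.1.2), and Hb that stays below 10.0 is itself informative. That stands: the documents do not support reading the endpoint as a mistaken attempt at new onset, and it should not be replaced.

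Falls are also covered elsewhere. The primary endpoint is change from Baseline with Baseline Hb as a covariate (SAP 6.11.2), changes are summarized by visit (6.12.2.3), and time to rescue is modeled with Baseline Hb (6.11.4.4.1). This is real but partial cover, since none of these reports new falls below the stated lines.

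A reader might infer that the rule biases the comparison between arms. It does not: randomization balances Baseline Hb in expectation, and the confidence interval allows for chance imbalance. What is lost is precision and clarity. A reader might also treat <9.0 like <10.0. The figures do not support that, because few subjects start below 9.0 and those who do are not near-certain cases. A low pre-dose value never counts by itself.

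Nor is new onset a full cure. With 16 values, many subjects starting at or above 10.0 will also dip below it, so proportions may stay high.

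**Conclusion.** The point holds mainly for <10.0 g/dL, and to a small extent for <9.0. The Table 3 proportion mixes low entry Hb with new falls, and its risk difference is diluted by up to the fraction starting below the line: 30% at b = 0.3 and 50% at b = 0.5. The <7.0 and <8.0 thresholds lie below the entry floor and are unaffected.

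The mechanism follows from the definitions alone. The size rests on assumed Baseline distributions, assumed new-fall rates of 70% and 55%, and every already-low subject being scored in both arms; if the arms differ in how long low Hb persists, dilution is less. These endpoints carry no margin, alpha or decision rule, and the primary conclusion does not depend on them. The change is still worth making because the data and the Baseline cut already exist.

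**What to change.** In SAP 6.12.2.1:
1. Keep the all-subject proportions in Table 3 as the specified endpoints.
2. For the <10.0 g/dL comparison, add the Baseline Hb category from 6.14 (<10.0, ≥10.0) to dialysis organization as Mantel-Haenszel strata. This improves precision and removes chance imbalance across that cut. It does not undo the dilution of the all-subject risk difference.
3. Add one supplementary table of new-onset Hb <10.0 and <9.0 g/dL, among subjects with Baseline Hb at or above the respective threshold. This addresses the dilution.

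No matching restriction is needed for >11.0 g/dL: entry caps mean screening Hb at 11.0, so it would remove almost nobody.

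The cost is SAP wording and one extra table. The new-onset <10.0 denominator falls to about 153 to 342 of 450 (450 × 0.34 to 450 × 0.76), and omits the subjects with the lowest entry Hb. Three organizations by two Baseline categories make six strata, some possibly small. The pooling rule in SAP 6.1 for strata under 30 can handle these; it should say that pooling is across organizations within a Baseline category, so that it does not undo the adjustment.
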